9.5.9 Patient-reported global change in disease activity

Sammenliknet med for 6 måneder siden, hvordan er din sykdomsaktivitet nå?

 Mye verre	 Verre	 Litt verre	 Uforandret	 Litt bedre	 Bedre	 Mye bedre
------------------------------------	--------------------------------	-------------------------------------	-------------------------------------	-------------------------------------	--------------------------------	------------------------------------

9.5.10 Patient-reported global change in activity impairment

Sammenliknet med for 6 måneder siden, hvordan er din evne til å utføre vanlige, daglige aktiviteter, utenom arbeid, nå?

 Mye verre	 Verre	 Litt verre	 Uforandret	 Litt bedre	 Bedre	 Mye bedre
------------------------------------	--------------------------------	-------------------------------------	-------------------------------------	-------------------------------------	--------------------------------	------------------------------------

9.5.11 Physical activity

Mosjon/ fysisk aktivitet

Med mosjon mener vi at du f.eks går tur, går på ski, svømmer eller driver trening/idrett.

1. Hvor ofte driver du mosjon?

Ta et gjennomsnitt

- Aldri
- Sjeldnere enn en gang i uka
- En gang i uka
- 2-3 dager i uka
- Omtrent hver dag

2. Hvor hardt mosjonerer du?

i Dette elementet vises kun dersom alternativet «En gang i uka», «Omtrent hver dag» eller «2-3 dager i uka» er valgt i spørsmålet «1. Hvor ofte driver du mosjon?»

Ta et gjennomsnitt

- Tar det rolig uten å bli andpusten eller svett
- Tar det så hardt at jeg blir andpusten og svett
- Tar meg nesten helt ut

3. Hvor lenge holder du på hver gang?

i Dette elementet vises kun dersom alternativet «En gang i uka», «Omtrent hver dag» eller «2-3 dager i uka» er valgt i spørsmålet «1. Hvor ofte driver du mosjon?»

Ta et gjennomsnitt

- Mindre enn 15 minutter
- 15-29 minutter
- 30 min - 1 time
- Mer enn 1 time

9.5.12 Patient satisfaction with care

Hvor fornøyd er du alt i alt med den behandlingen du har fått for din revmatiske sykdom?

				
Svært fornøyd	Fornøyd	Både og	Misfornøyd	Svært misfornøyd

9.5.13 Medication use

De siste 6 månedene, har du tatt medisin for din revmatiske sykdom som avtalt?

- Nei
- Ja

Hvis nei: Hvor mange ganger har du ikke tatt medisinen de siste 6 månedene? _____

De siste 6 månedene, har du fått kortison (injeksjon i ledd eller som tablett)?

- Nei
- Ja

Hvis ja: Hva var årsaken til at du fikk kortison: _____

De siste 6 månedene, har du brukt NSAIDs (betennelsesdempende medikamenter)?

- Nei
- Ja

Hvis ja: De siste 6 månedene, har du da brukt...

- NSAIDs som en kur over en periode?
- Enkelte NSAIDs tabletter nå og da?

Hvis ja: Hvilken NSAIDs type (navn) brukte du? _____

Hvis ja: Hvor mange milligram tok du per dag? _____

Hvis ja: Hvor mange dager brukte du NSAIDs?

- Mindre enn 1 dag per uke
- 1-3 dager per uke
- 4-5 dager per uke
- Mer enn 5 dager per uke
- Hver eneste dag

Hvis ja og som en kur: Hvilken dato startet du en NSAIDs kur? _____

Hvis ja og som en kur: Hvilken dato stoppet du en NSAIDs kur? . . .

De siste 6 månedene, har du brukt andre smertestillende medikamenter (andre enn betennelsedempende/NASAIDs)?

- Nei
- Ja

Hvis ja, Oppgi navn på medikament, hvor mange milligram du brukte per dag og antall dager:

9.5.14 Time use and costs related to consultations

1) Hvis du er i lønnet arbeid: Hva må du gjøre for å få fri fra arbeidet for å dra til Diakonhjemmet Sykehus

- Lønnet fravær fra arbeid
- Ulønnet fravær fra arbeid
- Jobber inn tiden senere/avspaserer
- Var utenfor arbeidstiden
- Tok ut ferie
- Andre ordninger

Hvilken annen ordning må du gjøre for å få fri? _____

2) Omrent hvor lang tid bruker du på å reise til Diakonhjemmet Sykehus (én vei)?

Oppgi antall minutter: _____

3) Omrent hvor lang er reiseveien til Diakonhjemmet Sykehus (én vei)?

Oppgi antall kilometer (km) én vei.

4) Hva slags transportmiddel bruker du vanligvis for å reise til Diakonhjemmet Sykehus?

Dersom du brukte flere typer transportmiddelet, sett kryss for transportmiddelet du bruker lengst (i form av distanse). (Sett ett kryss)

- Går/sykler
- Privat bil
- Buss/T-bane/tog
- Taxi
- Fly
- Annet:

Hvilket annet transportmiddel brukte du?:

5) *Hvis bil:* Kjører du bil selv eller blir kjørt?

Kjører bil selv Blir kjørt

6) *Hvis du blir kjørt:* Må vedkommende ta seg fri fra arbeidet? Nei Ja

9.5.15 Digital self-efficacy

Mestring av digitale tjenester og teknologi

Vurder dette på en skala fra "Svært dårlig" til "Svært godt". Sett kryss ved «Aldri prøvd» dersom du ikke har brukt tjenesten eller teknologien.

Hvor godt mestrer du:

	Aldri prøvd	Svært dårlig	Dårlig	Verken eller	Godt	Svært godt
Smarttelefon						
Nettbrett						
Datamaskin						
Å bruke app'er						
Innlogging med ID-porten (MinID, BankID, BankID på mobil, BuyPass)						
Digitale helsetjenester (f.eks. e-konsultasjon, videokonsultasjon, Helsenorge.no)						

9.5.16 eHealth literacy

20 items from 4 domains of the eHLQ³³: 1) using technology to process health information, 2) ability to actively engage with digital services, 3) feel safe and in control, 4) motivated to engage with digital services. Response options for all items range from 1 (strongly disagree) to 4 (strongly agree). The instrument cannot be shown due to license requirements.

9.5.17 Patient satisfaction with remote monitoring or patient-initiated care

22 items in the Service User Technology Acceptability Questionnaire (SUTAQ)³⁹ reported at the 18-months follow-up. While the remote monitoring arm will report all 22 items, the patient-initiated care arm will report on 3 of the 22 items (no. 1, 10 and 11). The usual care arm will not report on this questionnaire.

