6.1 Discontinuation of Study Intervention

Patients who for some reason withdraw from following the treatment protocol will be asked to continue follow-up in the study.

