6.2 Participant Discontinuation/Withdrawal from the Study

Patients have the right to withdraw from the study at any time for any reason. In the case that a patient decides to prematurely withdraw from the study, he or she should be asked if they can still be contacted for further information, so that a final evaluation can be made with an explanation of why the patient is withdrawing from the study, including assessment of possible adverse events. Although a subject is not obliged to give his or her reason(s) for withdrawing prematurely from a trial, the investigator should make a reasonable effort to ascertain the reason(s), while fully respecting the subject's rights. If possible, at the last visit of the patient all assessments of the "Early discontinuation of study visit" will be done.

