7.1.4 Regular visits

Assessments are as outlined in the Schedule of Activities and in section 7.2.

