7.1.7 Withdrawal visit

A withdrawal visit (early discontinuation) will include all assessments of a regular visit in addition to an assessment of reason for withdrawal and time of withdrawal.

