- **Euro Quality of Life 5 Dimensions 5 Levels (EQ5D-5L)** (Baseline, 6-, 12- and 18-months)
EQ-5D is a utility instrument for measurement of health related quality of life³⁵ and is applicable to a wide range of health conditions and treatments, it provides a simple descriptive profile and a single index value for health status.
- **Work Productivity and Activity Impairment (WPAI)** – item no. 6 on activity Impairment (NRS 0-10) (Baseline, 6-, 12- and 18-months).
- **Questions on physical activity from the HUNT study** (Baseline, 6-, 12- and 18-months) The HUNT questionnaire consists of 3 questions assessing frequency, intensity, and duration of physical activity in the past 7 days³⁶.
- **Sleep disturbance** (Baseline, 6-, 12- and 18-months) 1 item from the Pittsburgh Sleep Quality Index measuring sleep disturbance due to pain with four-point response categories ranging from "Not during the past month" to "Three or more times a week"³⁷.
- **Patient satisfaction with care** (Baseline, 6-, 12- and 18-months)
Satisfaction with the care provided (from patient experience questionnaires) includes one item with five point response options ranging from "Very satisfied" to "Very dissatisfied"³⁸.
- **Medication use** (Baseline, 6-, 12- and 18-months)
Questions on whether the patient has taken the TNFi medication as instructed, and if NSAIDs, glucocorticoid (oral or injections) or analgesics have been used.
- **Time and costs related to consultations** (Baseline)
The time being absent from work and potential travel costs related to consultations will be registered.

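### The SUTAQ is scheduled at month 18 and not clearly at the withdrawal visit, so patients who leave the study early may give no rating of the new strategies

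*Protocol*

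**What the plan says.** Protocol section 9.5.17 places the SUTAQ at one time point. It is "reported at the 18-months follow-up. While the remote monitoring arm will report all 22 items", while patient-initiated care answers items 1, 10 and 11 and usual care does not receive it.

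The content of the withdrawal visit is set by cross-reference. Section 7.1.7 states: "A withdrawal visit (early discontinuation) will include all assessments of a regular visit", to which the reason for and time of withdrawal are added. Section 7.1.4 defines the regular visit: "Assessments are as outlined in the Schedule of Activities and in section 7.2". Section 6.2 asks for the early-discontinuation assessments at the last visit, where possible.

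Patients who stop the strategy without leaving the study are treated differently. Section 6.1 states: "Patients who for some reason withdraw from following the treatment protocol will be asked to continue follow-up in the study".

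The protocol has other sources on satisfaction:
- Section 7.2.1 has a single item on satisfaction with care at baseline and at 6, 12 and 18 months.
- Section 2.3.4 lists interviews with 10-15 patients as the endpoint for perspectives on and satisfaction with remote monitoring.

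**The concern.** An acceptability questionnaire given only at the end of an 18-month strategy describes the people who stayed to the end. Dissatisfaction with the strategy is a plausible reason to leave. If it is a common one, the missing answers are related to what is being measured, and the reported acceptability is too favourable. Acceptability to patients is part of the argument for replacing scheduled visits, so the figure is likely to be cited.

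This is a question of data collection. Once a patient has left without being asked, no later analysis can supply the answer, so it cannot be left to the statistical analysis plan.

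**Working it through.** **Step 1. Is the SUTAQ part of the withdrawal visit?**

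- 9.5.17 names month 18 and no other time.
- 7.1.7 refers to a regular visit, and 7.1.4 refers to the Schedule and section 7.2.
- Section 7.2.1 lists the patient-reported measures with their timing. The SUTAQ is not among them.
- The Schedule marks a general patient-reported outcomes row in the column for extra visits and early discontinuation. The same row is marked at baseline, 6 and 12 months, when 9.5.17 does not schedule the SUTAQ. A mark in that row therefore does not show that the SUTAQ is given.
- Inclusion in Appendix 6 (patient-reported outcomes) does not settle it either. That appendix also holds measures confined to baseline, such as the BASFI and the items on time and costs of consultations.

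No text clearly puts the SUTAQ at the withdrawal visit.

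**Step 2. How large could the effect be?** The protocol states no figure on this point, so there is none to reproduce. Let d be the share leaving the study before month 18, ps and pl the shares satisfied among stayers and leavers, and a the share of leavers who answer.

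- Observed = [(1 − d)·ps + d·a·pl] / [(1 − d) + d·a]
- True = (1 − d)·ps + d·pl
- With a = 0, overstatement = d·(ps − pl)

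The arm size of 80 comes from the synopsis. The protocol gives no withdrawal rate and no satisfaction level for either group, so d, ps, pl and a are assumptions: ps = 80%, pl from 80% (leaving unrelated to satisfaction) down to 20%.

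| d | Stayers of 80 | a = 0, pl = 80% | a = 0, pl = 50% | a = 0, pl = 20% | a = 0.5, pl = 20% |
|---|---|---|---|---|---|
| 5% | 76 | 0 | 1.5 | 3.0 | 1.5 |
| 10% | 72 | 0 | 3.0 | 6.0 | 2.8 |
| 15% | 68 | 0 | 4.5 | 9.0 | 4.1 |
| 20% | 64 | 0 | 6.0 | 12.0 | 5.3 |

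Entries in the last four columns are percentage points of overstatement.

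Example at d = 10%, pl = 20%: true = 0.90·0.80 + 0.10·0.20 = 0.74. With a = 0, observed = 0.80, a gap of 6.0 points. With a = 0.5, observed = (0.72 + 0.01)/0.95 = 0.768, a gap of 2.8 points.

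**Step 3. Compare with sampling error.** With 72 respondents and 80% satisfied, the 95% half-width is 1.96·√(0.80·0.20/72) = 9.2 points. At 5-10% withdrawal the possible overstatement (0 to 6 points) is smaller than this. Unlike sampling error, it has a direction if leavers are less satisfied, and the interval does not show it.

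**The case against.** The strongest reply is that asking about acceptability at the end of exposure is an ordinary choice, that nothing in 9.5.17 is false, and that absence from section 7.2 proves little because the SUTAQ is missing there for month 18 as well. The Schedule row could be read to include it at early discontinuation. This stands to the extent that the text is ambiguous rather than an explicit exclusion. An ambiguous collection point still needs to be settled, and Step 1 shows why the generic row does not settle it.

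A second reply is that dissatisfaction is captured elsewhere. In part it is. The single satisfaction item is a section 7.2 measure and so belongs to the withdrawal visit, and the reason for withdrawal is recorded. Neither replaces the SUTAQ. The single item (9.5.12) asks about treatment received for the rheumatic disease, so a patient content with the drug but not with the follow-up model could answer favourably. Under 6.2 the patient need not give a reason for leaving. The interviews cover 10-15 patients, with no statement that leavers are included.

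A reader might also infer more than the protocol supports:

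- **That patients who dislike the strategy never answer.** Under 6.1, those who only stop following it are asked to remain in follow-up and can answer at month 18. Only those who leave the study are at risk of being missed.
- **That reported satisfaction is biased upward as a matter of fact.** No withdrawal rate or pattern of reasons is given, and the bias is zero if leaving is unrelated to satisfaction. The satisfaction endpoint named in the synopsis is the repeated item, not the SUTAQ.
- **That a comparison of the two new arms is distorted.** The protocol plans no SUTAQ comparison between them on the three shared items.
- **That the SUTAQ should also be given when a patient stops using the strategy.** The protocol defines no such moment. Section 5.3 grades compliance without a stopping date, and patient-initiated care has no scheduled visits or monitoring to stop.

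**Conclusion.** The point holds as a gap in data collection. Patients who leave the study before month 18 may be missing from the only questionnaire on acceptability of the new strategies, and acceptability may be overstated if dissatisfaction drives leaving. The size cannot be determined from the protocol. It is zero to several points under moderate assumptions, and 12 points at the extreme of the range examined (20% leaving, leavers 60 points less satisfied, none answering).

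The stakes are limited. The SUTAQ is not given to usual care, is not named as an endpoint in section 2.3.4, and has no bearing on the primary non-inferiority result or the safety comparison. The change is worth making because it is cheap and the lost answers cannot be recovered later.

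**What to change.** Amend 9.5.17 so that the SUTAQ is completed *at the 18-month follow-up, or at the withdrawal visit (7.1.7) if the patient leaves the study earlier*. Keep the same item set per arm: 22 items for remote monitoring and 3 for patient-initiated care. In the results, show withdrawal and month-18 responses separately, and give the number of patients without any SUTAQ in each of the two arms.

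The cost is one existing questionnaire added to a visit that is already planned, or sent through the survey link already in use. There are two small downsides. Respondents at withdrawal will have had less exposure than those at month 18, which is why the two sets should be shown separately. Patients who decline the withdrawal visit will still be missing, so the change reduces the problem without removing it. Under the assumptions above, if half of the leavers answered, the largest overstatement would fall from 6.0 to 2.8 points at 10% withdrawal and from 12.0 to 5.3 points at 20%.
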